10.4	INFORMED CONSENT PROCESS / HIPAA AUTHORIZATION	18
10.4.1	Alterations to Typical Consent Process	18
11	STUDY FINANCES	19
11.1	FUNDING SOURCE	19
11.2	CONFLICT OF INTEREST	19
12	PUBLICATION PLAN	19
13	REFERENCES	19

Study Summary

Title	Text-based intervention to minimize the time burden of routine cancer care
Short Title	TIME
IRB Number	
Protocol Number	UPCC 16921
Methodology	This is a randomized control trial of a text-based mobile intervention to triage patients prior to treatment with single agent checkpoint blockade. Our hypothesis is that the use of a text-based e-triage prior to treatment will lower total healthcare time relative to standard office visit.
Study Duration	1 year
Study Center(s)	Single center 
• Perelman Center for Advanced Medicine at the Hospital of the University of Pennsylvania
Objectives	
Primary:
 
• To measure and refine the performance of a text-based instrument to assess patient-reported immunotherapy toxicity by determining sensitivity and specificity against the gold standard-in person provider assessment as documented in the electronic medical record (EMR).• To compare total care times, defined as time spent commuting to, waiting for, and receiving care, associated with a text-based e-triage system versus standard office visit among patients with advanced cancer receiving immunotherapy over a three-month period. 
Secondary:
 
• To determine whether a text-based e-triage affects healthcare quality of life as well as treatment and provider satisfaction.• To determine whether a text-based e-triage affects total number of emergency department visits and hospitalizations.
Number of Subjects	Up to 100 patients will be enrolled for the pilot study. 176 will be enrolled for the randomized control trial.
Main Inclusion and Exclusion Criteria	
Inclusion criteria
 
• Age 18 or older and able to give informed consent• English speaking• Receiving single-agent PDL-1/PD-1 checkpoint blockade• Diagnosed with a solid tumor malignancy• Access and ability to use a mobile phone with text-messaging capabilities•

CONFIDENTIAL

Intervention	
Pilot study to optimize instrument performance:
 
 Prior to their scheduled immunotherapy infusion, consented patients will receive a text-based e-triage questionnaire. Following completion of the questionnaire, patients will proceed to their in-person assessment and providers will screen patients for potential immune related adverse events per routine care. Performance of the e-triage system will then be compared to the provider progress note documented in the EMR as the gold standard. 
Randomized control trial:
 
 Treatment arm: For patients in the intervention arm, symptoms and laboratory results will be assessed using the text-based e-triage 96 hours prior to their intended infusion date. The e-triage will consist of a standardized questionnaire and algorithm to evaluate symptoms and laboratory values. Patients with acceptable labs and minimal or no symptoms can opt to proceed directly to their immunotherapy infusion without an in-person office assessment. Usual Care: Patients in the usual care arm will receive standard of care symptom monitoring including an in-person office assessment prior to their scheduled immunotherapy infusion.
Statistical Methodology	
Pilot:
 
 Sensitivity and specificity will be calculated along with exact 95% confidence intervals (CIs). Sensitivity will be calculated as the proportion of patients with toxicity captured by the text-based e-triage among patients with toxicity as documented by the provider in the EMR. Specificity will be calculated as the proportion of negative e-triage screens among patients without symptoms as documented by the provider in the EMR. 
Randomized control trial:
 
 The primary analyses will be Intent-to-Treat, with the primary outcome (total care time measured over three months) compared using a two-sample t test, or Wilcoxon test if normal distribution assumption is violated. A multivariate linear regression model will adjust for potential confounders. As a secondary analysis, “as treated” analyses will be performed to account for permissive non-adherence to the triage assignment. Standard descriptive statistics will be used to describe patient factors associated with more frequent triage non-adherence. Secondary endpoints include: total wait time measured over three months or at least 3 office visits, total number of hospitalization/emergency department encounters, patient satisfaction [The Patient Satisfaction Questionnaire Short Form (PSQ-18)]¹, provider satisfaction (Net-Promoter Score)^{2,3}, and health related quality of life [Functional Assessment of Cancer Therapy-General (FACT-G)⁴]. Total wait time and number of hospitalizations will be compared between groups using Wilcoxon rank sum test. The rest of the secondary endpoints will be measured at multiple time points and longitudinal linear mixed-effects model will be used to compare the group difference over time.
Data and Safety Monitoring Plan	
Trial oversight will be conducted by the University of Pennsylvania Institutional Review Board. Safety will be monitored on an ongoing basis by the PI, study team, and institutional experts not involved in the study.

CONFIDENTIAL

Background and Study Rationale

This study will be conducted in full accordance with all applicable University of Pennsylvania Research Policies and Procedures and all applicable Federal and state laws and regulations including the following regulations as they apply: 45 CFR 46, 21 CFR Part 50. All episodes of noncompliance will be documented.

1 Introduction

1.1 *Background and Relevant Literature*

Patients with advanced cancer spend a substantial portion of their time receiving healthcare, often despite limited survival benefit⁵⁻¹¹. We have previously demonstrated that patients with advanced pancreas cancer spend 10% of their remaining survival time receiving healthcare, with greater than 50% spent commuting or in waiting rooms⁸. Additionally, inefficiencies in care delivery reduce access to both clinicians and infusions suites. This problem is only projected to get worse as the number of patients with cancer grows¹²⁻¹⁴. Within the Perelman clinics we have seen a rise in visits from 78,525 to 89,117 in three years with a corresponding increase in new patient wait times from 17.5 to 38.1 days. Furthermore, patients currently wait an average of 30 minutes to receive their cancer treatment in part due to high volume of care and need for same day labs, orders, and drug preparation. Given that access to care, including patient wait time, is critical determinant of patient satisfaction^{10,15-21}, there is need for innovative strategies that mitigate time toxicity while delivering high quality care.

During the COVID-19 pandemic, oncologists have had to rapidly transform cancer care delivery²²⁻²⁵. Telemedicine has emerged as the primary strategy to ensure patient and provider safety²⁶. eHealth, a subset of telemedicine, supports traditional healthcare practice through email, portals or text²⁷. The use of digital technologies to monitor patient reported outcomes (PRO) in oncology is well established, having been shown to improve patient provider communication, satisfaction, and symptom distress²⁸⁻³⁷. While digital technologies have primarily focused on capturing PROs, none have yet been applied as a tool to reduce the time-burden associated with cancer care. eHealth initiatives can streamline care, thereby providing more patient-centered cancer treatment.

In this research, we propose a randomized controlled trial (RCT) of a text-based mobile intervention to triage patients prior to cancer treatment. We will leverage WayToHealth[®], an established technology platform shown to successfully facilitate patient and provider communication through texting for both research and clinical care³⁸⁻⁴¹. The overall objective is to determine whether this intervention can safely lessen the need for in-person office visits, thereby lowering care time, while also preserving patient satisfaction and treatment outcomes. Results from this study will shift the care delivery paradigm toward more patient-centered cancer care, improving accessibility and the patient experience.

2 Study Objectives

The primary objective is to test whether a text-based e-triage can safely identify patients who can proceed directly to their immunotherapy infusion without a preceding in-person office assessment.

2.1 *Specific aims*

The specific aims of this single center randomized project are to:

AIM 1: To measure and refine the performance of a text-based instrument to assess patient-reported immunotherapy toxicity by determining sensitivity and specificity against the gold standard in-person provider assessment as documented in the electronic medical record.

H1: In this cross-sectional study, a text-based e-triage can successfully identify patients experiencing toxicity with a sensitivity of 100%.

AIM 2: To compare total care times, defined as time spent commuting to, waiting for, and receiving care, associated with a text-based e-triage system versus standard office visit among patients with advanced cancer receiving immunotherapy over three months or at least three infusion visits.

CONFIDENTIAL

H2: In this randomized clinical trial, the use of a text-based e-triage prior to treatment will lower total care time relative to standard office visit.

In addition to the primary aims, we will also explore: 1) the impact of the intervention on healthcare quality of life and patient/provider satisfaction; 2) the effect of the intervention on total number of emergency department and hospitalizations across both study arms; 3) total wait times over a three-month period associated with the intervention versus standard of care.

3 Investigational Plan

3.1 General Design

This study consists of a rapid pilot validation (aim 1) and a randomized control trial (aim 2) to assess the performance and efficacy of a text-based e-triage to minimize the time toxicity of cancer care. The rapid pilot validation will consist of a cross-sectional study to measure and refine the performance of a text-based instrument to assess patient-reported immunotherapy toxicity by determining sensitivity and specificity against the gold standard in-person provider assessment as documented in the EMR. The randomized control trial will involve randomizing patients 1:1 to either the e-triage arm or standard of care. Total care times, defined as time spent commuting to, waiting for, and receiving cancer care, will be measured, and compared across both study arms over a three-month period or at least three infusion visits. See appendix A.

3.2 Allocation to Interventional Group

Patients will be randomized 1:1 to either the intervention (e-triage) or control (standard of care) arms using a randomization sequence created using the WaytoHealth® platform.

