3.3 Study Measures

AIM 1 Pilot study:

- **E-triage:** The e-triage will consist of 16 questions, modified from the validated NCI Pro-CTCAE™, which will be sent to patients via WaytoHealth®'s two-way texting system 96 hours prior to their scheduled immunotherapy infusion (see appendix B). Questions will pertain to common or emergent immune related adverse events as defined by the NCCN guidelines and two senior disease experts⁴²⁻⁴⁴. Patients will be prompted via text to measure the presence and severity of symptoms over the week prior. A final question will be included to capture any additional symptoms patients wish to disclose.
- **NCI Pro-CTCAE™:** A subset of patients may be asked to fill out a subset of the NCI PRO-CTCAE™, a set of validated questions for the collection of patient-reported outcomes to capture symptomatic adverse events in patients on cancer clinical trials, in order assess construct validity.
- **Definition of gold standard:** Patient reported toxicity captured by the text-based instrument will be compared to provider reported toxicity as documented in the EMR as the gold standard. To assess provider reported toxicity, standardized abstraction protocols will be developed by the PI and implemented by trained research staff.

AIM 2 Randomized control study:

- **Care time:** Care time will be defined as total time spent commuting to and receiving cancer care (including time spent obtaining labs). This will be captured using a combination of time-stamp information abstracted from AirFinder®, a real time patient located system deployed in the Perelman Cancer Clinics, and self-reported time for commuting and time spent obtaining local labs. Commute times will also be estimated using the patient's home address geocoded using ArcGIS software.
- **Emergency department and hospitalization rates:** Total number of emergency department visits and hospitalizations will be collected using data abstracted from the Penn electronic medical record during a 3 month follow-up window as well as through patient check-ins with study staff during routine infusion visits to account for care received outside the Penn system.

CONFIDENTIAL

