3.4.1 Primary Study Endpoint

AIM 1 Pilot: To assess the performance of the text-based e-triage system sensitivity and specificity with a gold standard will be determined.

AIM 2 Randomized control trial: The primary endpoint will be cumulative care time associated with cancer treatment, measured over a over three months or at least 3 infusion visits. We will define care time as total time spent commuting to and receiving care (including time spent obtaining labs).

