3.4.2 Secondary Study Endpoints

AIM 2 Randomized control trial: Secondary endpoints will include total wait time (see attached study flowchart), total number of ED visits and/or hospitalizations, health related quality of life utilizing the FACT-G⁴, treatment satisfaction with the PSQ-18¹, and providers satisfaction using the net-promoter score^{2,3}.

4 Study Population and Duration of Participation

4.1 *Duration of Study Participation*

AIM 1 Pilot study: The duration of study participation will be 2 months from the date of enrollment.

AIM 2 Randomized control study: The duration of study participation will be the time it takes to complete 3 infusion visits, approximately 3 months..

4.2 *Total Number of Subjects and Sites*

Penn (Perelman Center for Advanced Medicine floors 2,3,4) will be the only site recruiting patients. For the pilot study we will enroll up to 100 patients over a 2-months. For the randomized control trial, to have 160 evaluable subjects, with an expected 10% drop out rate, we plan to enroll 176 patients.

4.3 *Inclusion Criteria*

AIM 1: Pilot participants:

- Over 18 years of age
- Access to mobile device with text messaging capabilities
- Receiving single agent PDL-1/PD-1 targeted immune checkpoint blockade for any solid malignancy
- Treating oncologist is at Penn's Abramson Cancer Center

AIM 2: Randomized control trial participants:

- Over 18 years of age

CONFIDENTIAL

- Receiving single agent PDL-1/PD-1 targeted immune checkpoint blockade for any solid malignancy
- Access to and ability to use a mobile phone with texting capabilities

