6.2 Statistical Methods

Aim 1 Pilot study: Sensitivity and specificity will be calculated along with exact 95% confidence intervals (CIs). Sensitivity will be calculated as the proportion of patients with toxicity captured by the text-based e-triage among patients with toxicity as documented by the provider in the EMR. Specificity will be calculated as the proportion of negative e-triage screens among patients without symptoms as documented by the provider in the EMR. We will additionally be performing a series of psychometric analyses including response distribution to assure responses are not skewed, item-scale correlation, internal consistency, floor and ceiling effects and item reduction as well as response rates.

Table 2. Power to detect reduction in total care time (N=160)	
Reduction in care time	Power
35%	68%
40%	79%
45%	88%
50%	93%

AIM 2 Randomized control study: Standard descriptive statistics will be calculated to compare patient characteristics for the intervention arm versus the control arm, such as medians and interquartile ranges for continuous variables and frequencies and proportions for categorical variables. These characteristics will be compared between the two groups using the Wilcoxon rank sum test for continuous variables and the chi squared or Fisher's exact test for categorical variables. We expect these characteristics will be similarly distributed between the intervention groups due to randomization, but in the case of imbalance, they may be adjusted in the multivariable model of the outcome.

The primary analyses will be Intent-to-Treat, with the primary outcome (total care time) compared using a

CONFIDENTIAL

two-sample t test, or Wilcoxon test if normal distribution assumption is violated. A multivariate linear regression will be used to adjust potential confounders including demographics (age, gender, race, SES), comorbidities (Elixhauser comorbidity index), treatment intent (curative versus palliative), and performance status. The final model will be established using stepwise forward regression based on 10% change in effect estimate for intervention. As a secondary analysis, “as treated” analyses will be performed to account for permissive non-adherence to the triage assignment. Standard descriptive statistics will be used to describe patient factors associated with more frequent triage non-adherence.

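### Commute time, and infusion interval if the window is three months, drive cumulative care time, but the primary comparison adjusts for neither: precision is lost, validity is not

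*Protocol*

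**What the plan says.** **Allocation.** Protocol 3.2 states that "Patients will be randomized 1:1 to either the intervention (e-triage) or control (standard of care) arms using a randomization sequence" created on the texting platform. It mentions no stratification factor or blocking, and neither does any other section or the SAP.

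**Eligibility.** Protocol 4.3 admits patients "Receiving single agent PDL-1/PD-1 targeted immune checkpoint blockade for any solid malignancy". It limits neither infusion interval nor distance from the clinic.

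**Endpoint.** Protocol 3.4.1: "The primary endpoint will be cumulative care time associated with cancer treatment, measured over a over three months or at least 3 infusion visits". The same section, like 3.3, counts commuting as part of care time. Section 3.3 adds: "Commute times will also be estimated using the patient's home address geocoded using ArcGIS software".

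**Window.** The documents are not uniform:
- The Study Summary (Statistical Methodology), Protocol 6.3.2 and SAP 1.3.2 describe the primary outcome as measured over three months.
- Protocol 4.1 says "The duration of study participation will be the time it takes to complete 3 infusion visits, approximately 3 months", and 5.2.2 speaks of three cycles.
- Protocol 2.1, 3.1 and 3.4.1 join the two with an or.

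**Analysis.** The primary test in Protocol 6.2 and SAP 1.2 is a "two-sample t test, or Wilcoxon test if normal distribution assumption is violated". A regression then adjusts for confounders, including "demographics (age, gender, race, SES), comorbidities (Elixhauser comorbidity index), treatment intent (curative versus palliative), and performance status". Its final model is chosen by forward selection on a 10% change in the intervention estimate.

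**The concern.** Two features that exist before assignment feed directly into the outcome. The first is how far the patient lives from the clinic, since every trip carries a commute that is counted. The second, under a three-month window, is how often the regimen brings the patient in. E-triage can remove the office assessment, but not the infusion trip.

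The primary analysis leaves variation from both sources in the error term. If one arm happens to receive more long-distance or frequently infused patients, the arm difference shifts for reasons unrelated to e-triage. Even with balanced arms, the confidence interval is wider than it need be. The trial is planned at just under 80% power and already intends to geocode home addresses, so it would be giving up precision that costs almost nothing to obtain.

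**Working it through.** **Inputs from the documents** (Protocol 6.1, SAP 1.1): control mean 130 h, SD 118 h, target difference 130 − 78 = 52 h, 80 per arm, type I error 0.05 (sidedness not stated; two-sided reproduces the figure).

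**1. Reproduce the stated power.**
- SE = 118 × √(2/80) = 18.66 h.
- Power = Φ(52/18.66 − 1.96) = 79.6% (normal); the noncentral t gives 79.1%. The stated 79% reproduces.
- Table 2 (68/79/88/93%) also reproduces: 67.9/79.1/87.6/93.4% with the t distribution.

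**2. Share of variance due to interval.** The documents give no interval mix. *Assumption:* intervals of 2, 3, 4 and 6 weeks in shares of 10/40/30/20%, a 12-week window, and care time proportional to infusion trips.
- Trips 6, 4, 3, 2: mean 0.6 + 1.6 + 0.9 + 0.4 = 3.5; mean square 13.5; variance 13.5 − 3.5² = 1.25; squared CV 1.25/12.25 = 0.102.
- The plan's squared CV for total care time is (118/130)² = 0.824.
- Share = 0.102/0.824 = **about 12%**.
- If the six-weekly patients are followed to three infusions (trips 6, 4, 3, 3): mean 3.7; variance 14.5 − 3.7² = 0.81; squared CV 0.81/13.69 = 0.059; share = 0.059/0.824 = **about 7%**.
- If the window is exactly three infusions for everyone, the scheduled trip count is constant and interval explains none of it.

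Other mixes, using 13 weeks divided by the interval as the trip count, run from about 2% (half 3-weekly, half 4-weekly) to about 26% (equal thirds 2-, 4- and 6-weekly).

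**3. Consequence for the primary comparison.** With R² the share explained, the SD of the chance-imbalance contribution is 18.66 × √R², and the adjusted SE is 18.66 × √(1 − R²).

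| R² | Chance-imbalance SD (h) | Adjusted SE (h) | Power for 52 h (normal) |
|---|---|---|---|
| 0 (as planned) | – | 18.66 | 79.6% |
| 0.07 | 4.9 | 17.99 | 82.4% |
| 0.12 | 6.5 | 17.50 | 84.4% |

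The interval narrows by 1 − √(1 − R²), about 4% and 6%.

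**4. Commute.** It is part of the outcome by definition, but the documents give no spread of commute times, so no share can be assigned. As a what-if only, a combined R² of 0.20 or 0.30 for interval plus commute would give power of 87.6% or 91.5%.

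**5. Would listing the covariates be enough?** No. The regression is not the primary test, and its covariates must pass the 10%-change rule. In a simulation (160 patients, true difference 52 h, SD 118 h, one normally distributed baseline covariate), a covariate with R² of 0.10, 0.20 or 0.30 passed in about 38%, 54% or 62% of trials. A useful covariate that happens to be balanced tends to be left out, although it would still narrow the interval.

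**The case against.** The strongest reply has four parts.

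*The interval effect depends on the window.* If follow-up is three infusions, as Protocol 4.1 and 5.2.2 suggest, the trip count is the same for everyone and interval mainly changes calendar length. This stands: the interval half of the point is conditional. The commute half holds under either window.

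*The effect is small and the trial remains valid.* This also stands. A chance-imbalance SD of 5-7 h is modest beside an SE of 18.7 h and a 52 h target. A reader might infer that the comparison is biased or the power figure wrong. Neither follows: randomization protects the average comparison and the type I error, the 79% reproduces, and the SD of 118 h may already contain this variation.

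*Adjustment is already allowed.* The covariate list is introduced as open, and imbalanced characteristics may be adjusted for. That permits later adjustment but prespecifies neither variable, and the primary test stays unadjusted. SES is at best a weak proxy for distance.

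*Section 3.2 does not rule out stratification.* Correct. A reader might infer that the sequence is unstratified, but the text is only silent, and the platform could stratify without the protocol saying so.

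**Conclusion.** The point holds as a missed, inexpensive gain in precision. Commute is inside the endpoint, the plan already geocodes it, and the primary analysis ignores it. Under a three-month window the same is true of planned infusion interval.

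On the assumed mix and the plan's own SD and mean, interval alone explains about 7-12% of variance. That is a chance-imbalance SD of about 5-7 h, and power of about 82-84% rather than about 80% after adjustment. These figures rest on an interval mix that the documents do not supply, on care time being proportional to trips, and on a three-month window. Commute would add to them by an unknown amount.

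A reader might infer a much larger share for interval by assuming little variation in time per trip. With a per-trip CV of 0.4, the same mix gives 0.102/(0.102 + 0.16 + 0.016) = 37%. But the total CV is then √0.278 = 0.53, an SD of about 69 h on a mean of 130 h, well below the planned 118 h. The plan's own figures do not support that reading.

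**What to change.** In Protocol 6.2 and 6.3.2 and SAP 1.2 and 1.3.2, before outcome data are examined:

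- Prespecify a linear model of total care time on arm, geocoded one-way commute time (home address at randomization) and planned infusion interval at randomization. Always include both covariates, exempt from the 10%-change rule.
- Use this model for the primary estimate and confidence interval. An SD of 118 h on a mean of 130 h implies right skew, so specify robust standard errors or a suitable transformation.
- Keep the unadjusted t or Wilcoxon comparison as a sensitivity analysis.
- Reconcile the window wording, since it decides how much the interval term can contribute.

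In Protocol 3.2, state whether the sequence is stratified. If randomization has not begun, stratifying by planned interval is an option. Stratification without adjustment would not narrow the interval of an unadjusted t test, so it does not replace the model.

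**Cost.** No extra patients or visits. Planned interval must be recorded at baseline, which no section now provides for, and the SAP needs a few sentences. Commute needs no new measurement, because 3.3 already plans the geocoding. Protocol 8.1 first limits the identifiers collected to name, date of birth and record number, then mentions address among those encrypted; that wording should be aligned with 3.3.
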